### **1.3 Compliance Statement**

This study will be conducted in full accordance all applicable local Policies and Procedures and all applicable Federal and state laws and regulations including 45 CFR 46 and the HIPAA Privacy Rule. All episodes of noncompliance will be documented. The investigators will perform the study in accordance with this protocol, will obtain consent and assent, and will report unanticipated problems involving risks to subjects or others in accordance with The Children's Hospital of Philadelphia IRB Policies and Procedures and all federal requirements. Collection, recording, and reporting of data will be accurate and will ensure the privacy, health, and welfare of research subjects during and after the study.

## **2 STUDY OBJECTIVES**

### **2.1 Primary Objective (or Aim)**

Aim 1: To determine the overall infection incidence rate within the first year following completion of therapy for acute lymphoblastic leukemia and compare that rate with the rate of infections occurring in age- and sex-matched healthy control patients during the same time period.

- Sub-aim: To examine infection incidence in patients who received the monoclonal antibody blinatumomab as part of their ALL treatment protocol versus that of patients who did not receive blinatumomab.

### **2.2 Secondary Objective (or Aim)**

Aim 2a: To describe total IgG levels and specific seroprevalence for pneumococcus, varicella, and measles at approximately 3, 6, and 12 months following completion of therapy in patients with ALL

Aim 2b: To describe B and T lymphocyte subset recovery, specifically CD4+ Tfh, using PMBCs at approximately 3, 6 and 12 months following completion of ALL

- Sub-aim: To examine the immune function markers as outlined above in patients who received the monoclonal antibody blinatumomab as part of their ALL treatment regimen versus patients who did not receive blinatumomab.

## **3 INVESTIGATIONAL PLAN**

### **3.1 General Schema of Study Design**

This is a prospective, multicenter observational study that will assemble a cohort of approximately 115 patients that recently completed or are about to complete ALL therapy at

---

one of several pediatric hematology/oncology centers in the US (CHOP, Lurie Children's Hospital of Chicago, Seattle Children's Hospital, DeVos Children's Hospital, Children's Hospital at Vanderbilt, Christus Children's Hospital (Baylor College of Medicine), and Children's Hospital Los Angeles), including a sub-cohort of 20-25 patients who received blinatumomab as part of their chemotherapy regimen. The same 115 individuals will contribute to both Aim 1 and Aim 2 (Figure 1 and Figure 2). Only patients receiving care at a participating site will be eligible for enrollment in this cohort.

### **3.2 Total Number of Study Sites/Total Number of Subjects Projected**

#### **3.2.1 Duration of Study Participation**

Patients will be followed from the date of enrollment until the first of the following events: approximately one year from completion of therapy, loss to follow-up or death.

Data abstraction from the medical record will be used to determine their end of therapy date. Their medical record will also be examined to collect specified relevant data related to reported infectious history as well as vaccination history. The in-person enrollment visit will require approximately one-hour of direct contact with the patient and caregiver to obtain consent (and when necessary, assent) and to complete the enrollment encounter. Once enrolled, followed by in-person visits at approximately 3, 6, and 12 months. At these visits an interim infectious history will be obtained and patients will have blood drawn for research assays as detailed below. These visits and the associated blood draw will be aligned with regularly scheduled oncology visits. The blood specimen will be drawn by the oncology nursing team and/or phlebotomy and whenever possible will be obtained at the same time as a clinical blood draw. Between in-person visits, study staff will contact caregivers for enrolled patients via phone call, text message, or email (as preferred by caregiver) to capture interim infection events. If text message or email is used to contact caregiver, but additional information is needed, a phone call will be made when necessary.

At the end of participants' study follow-up periods, age- and sex-matched healthy control patients will be identified from the CHOP Pediatric Research Consortium (PeRC) for comparison. Three controls will be randomly selected from a list of otherwise healthy individuals with similar age and sex and matched to each ALL patient enrolled. Infection events will be captured for these controls during the same time period the study participant was followed to compare the rate of infection events in the post-ALL therapy cohort with that of matched healthy controls.

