### Setting/Participants:

---

This is a multicenter study at several pediatric hematology/oncology centers in the US (CHOP, Lurie Children's Hospital of Chicago, Seattle Children's Hospital, Helen DeVos Children's Hospital, Children's Hospital at Vanderbilt, Christus Children's Hospital (Baylor College of Medicine), and Children's Hospital Los Angeles). The study cohort will consist of up to 110 evaluable patients prospectively enrolled over the course of this study. Eligible patients include: Children, adolescents, and young adults diagnosed with B or T ALL at age 12 months or older; have completed up-front ALL therapy within the past three months or will complete ALL therapy in the upcoming three months, and are three years of age or older at time of enrollment. Patients who have a diagnosis of infant ALL, evidence of disease relapse, have a history of primary immunodeficiency (except related to Down Syndrome), received a stem cell transplant or cellular immunotherapy, or prior malignancy or condition requiring chemotherapy other than for current ALL diagnosis will be excluded.

All matched healthy control patients will be selected from the Children's Hospital of Philadelphia's Pediatric Research Consortium patient population regardless of where their matched ALL cohort patient was enrolled in the study.

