**Study Measures:**

Aim 1 will capture any infection documented at any inpatient or outpatient encounter documented by the managing medical team in the first year after completing ALL chemotherapy. An incident infection rate will be calculated for the cohort and compared with that of age- and sex-matched healthy controls during the same time period. The secondary aim will assess the seroprevalence for pneumococcus, varicella and measles among study subjects at approximately 3, 6, and 12 months after completion of therapy. This aim will also describe B and T lymphocyte subset recovery at these same timepoints. The outcomes for Aim 1 and Aim 2 will be described by certain demographic characteristics and underlying diagnoses, as well as ALL treatment protocol. Additionally, laboratory reports will be prospectively collected. These data will serve to define the infection rate in the first year after completing ALL chemotherapy and inform immune recovery overall and to specific vaccine preventable illnesses (i.e. varicella, measles, and pneumococcus).

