### **3.3 Study Population**

#### **3.3.1 Inclusion Criteria for ALL Cohort**

1. Children, adolescents, and young adults ages 3 years to 31 years diagnosed with B or T ALL at age 12 months or older
2. Completed ALL chemotherapy within the past three months or will complete ALL chemotherapy in the upcoming three months (+/- 4 weeks)
  - **Blinatumomab sub-cohort (n = 20-25):** received ALL chemotherapy including the monoclonal antibody blinatumomab
3. Three years of age or older at time of enrollment.

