### **4.3 Observational Period**

Patients will be followed up to approximately one year from enrollment. Patients will also have specified relevant data collected from prior to the day of enrollment. During the observational period, the following will be performed:

- Data abstraction from the Medical Record

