### 6.3 Statistical Methods

#### 6.3.1 Baseline Data

Baseline and demographic characteristics will be summarized by standard descriptive summaries. Categorical variables will be summarized by frequencies while continuous variables will be summarized by using mean, standard deviation, median, twenty-fifth and seventy-fifth percentiles, minimum and maximum.

#### 6.3.2 Analysis of Aim 1

Aim 1 (total number of unique infections identified within the first year after completing chemotherapy) will be reported as a rate per 1000 follow-up days. This rate will be reported for the entire cohort, by study site, and by demographics (e.g., age, race, gender). This outcome will also be reported within subsets of infection type (i.e., microbiologically documented infections and bacterial sinopulmonary infections) also reported as a rate per

---

1000 follow-up days for the entire cohort, by study site and by specific demographic variables. All infection rates will be reported as a post estimate with 95% confidence intervals. Patients will be censored at time of lost to follow-up or death.

Infection rates for enrolled patients will also be compared to those of controls matched on age and sex selected from the CHOP Pediatric Research Consortium (PeRC). Three healthy controls will be selected for each participant for a case to control ratio of 1:3. Control patient infection data will be obtained for the same follow-up time period as that of the matched case patient in order to match risk for infection from seasonal pathogens (e.g., if a case patient completed ALL therapy and enrolled in the study in January 2023, infection data for the matched controls would be collected from January 2023 through December 2023, the same follow-up period as that of the case patient). All control patients will be randomly selected, and control data will be collected when follow-up is complete for participants in the ALL cohort.

Infection rates will also be generated for patients who received blinatumomab as part of their chemotherapy regimen and those who did not receive blinatumomab.

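### The Aim 1 rate targets the first year after therapy, but its follow-up days are undefined and the two stated follow-up windows match neither that year nor each other

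*Combined protocol and SAP*

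**What the plan says.** **Target.** Sections 2.1, 6.1 and 6.4 all place the Aim 1 rate in the first year after completion of therapy. The abstract (Study Measures) counts "any infection documented at any inpatient or outpatient encounter documented by the managing medical team in the first year after completing ALL chemotherapy".

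**Numerator and denominator.** Section 6.3.2: "total number of unique infections identified within the first year after completing chemotherapy) will be reported as a rate per 1000 follow-up days". It gives no first day and no last day for those follow-up days. It adds only that patients are censored at loss to follow-up or death.

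**Follow-up.** Section 3.2.1: "Patients will be followed from the date of enrollment until the first of the following events: approximately one year from completion of therapy", with loss to follow-up and death as the other ends. Section 4.3: "Patients will be followed up to approximately one year from enrollment".

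**Enrollment.** The abstract (Setting/Participants) admits patients who "have completed up-front ALL therapy within the past three months or will complete ALL therapy in the upcoming three months". Section 3.3.1 adds a four-week allowance: "Completed ALL chemotherapy within the past three months or will complete ALL chemotherapy in the upcoming three months (+/- 4 weeks".

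**Data before enrollment.** Section 3.2.1 has the medical record examined for infectious history, section 4.2.1 takes an infectious history at the baseline visit, and section 4.3 provides for some data from before the enrollment day. None of these says whether such events, or the matching days, enter the rate.

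**Controls.** Section 6.3.2: "Control patient infection data will be obtained for the same follow-up time period as that of the matched case patient". Section 3.2.1 gives controls the period over which the participant was followed. The abstract (Study Design) and section 6.3.4 call it the same one-year period. The one worked example is a patient for whom completion and enrollment coincide: "if a case patient completed ALL therapy and enrolled in the study in January 2023".

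**The concern.** A rate needs events and person-time drawn from the same window. Here the events are tied to end of therapy, while the only stated start of follow-up is enrollment, which can lie months before or after it. The two stated end dates then disagree by the same gap. The three windows coincide only for a patient enrolled on the day therapy ends.

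For early enrollees, no rule removes on-therapy days from the denominator. Section 1.2 itself reports that pneumococcal risk is highest during maintenance chemotherapy, so on-therapy time should not be mixed with post-therapy time. For late enrollees, nothing says whether the weeks between end of therapy and enrollment count, as events or as days. This is the primary endpoint, and section 6.4 expects clinicians to use it when advising families. The 4.3 wording also affects data collection, because a site that follows it literally stops an early enrollee before the post-therapy year is over.

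**Working it through.** **Inputs.** End of therapy is day 0 and the target window is days 0 to 365. Enrollment day e lies between -M and +M. M is about 91 (three months, abstract) or 91 + 28 = 119 (adding the four weeks in 3.3.1). The ALL rate is 1.88 per person-year (6.4).

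**The plan's own figures.** 1.88 × 1000/365 = 5.15 per 1000 days. 1.88/1.30 = 1.446 and 1.88/0.99 = 1.899, which agree with the stated rate ratios of 1.45 and 1.90. None of these is disputed.

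**Followed windows, by arithmetic on the stated rules.** Under 3.2.1 the window runs from e to 365 and lasts 365 - e days. Under 4.3 it runs from e to e + 365.

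| e | 3.2.1 window | Days | On therapy | 4.3 window | Days outside 0 to 365 |
|---|---|---|---|---|---|
| -119 | -119 to 365 | 484 | 119 (25%) | -119 to 246 | 119 of 365 (33%) |
| -91 | -91 to 365 | 456 | 91 (20%) | -91 to 274 | 91 of 365 (25%) |
| 0 | 0 to 365 | 365 | 0 | 0 to 365 | 0 |
| +91 | 91 to 365 | 274 | 0 | 91 to 456 | 91 of 365 (25%) |
| +119 | 119 to 365 | 246 | 0 | 119 to 484 | 119 of 365 (33%) |

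Under 4.3 an early enrollee is last followed at day 246 to 274, about month 8 to 9 after therapy (246/365 × 12 = 8.1; 274/365 × 12 = 9.0). Under 3.2.1 the followed period ranges from 246 to 484 days, so it is not the one-year period described for controls.

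**One patient at the edge of the window.** If all first-year infections are divided by 3.2.1 days, the true rate is multiplied by 365/(365 - e). For e = -119 this is 365/484 = 0.75 (5.15 becomes 3.88 per 1000 days). For e = +119 it is 365/246 = 1.48 (7.64 per 1000 days).

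**Whole cohort, illustration only.** Two assumptions are not in the documents: the rate is constant at 1.88, and enrollment is uniform over -M to +M.

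| Events counted | Days counted | Factor | M = 91 | M = 119 |
|---|---|---|---|---|
| All in days 0 to 365 | 3.2.1 | 365/365 | 1.88 | 1.88 |
| All in days 0 to 365, charts reviewed to day 365 | 4.3 | 365/365 | 1.88 | 1.88 |
| In days 0 to 365 and after enrollment | 3.2.1 | (365 - M/4)/365 | 1.76 | 1.73 |
| In days 0 to 365 and inside the 4.3 window | 4.3 | (365 - M/2)/365 | 1.65 | 1.57 |

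For M = 119 the last two factors are 335.25/365 = 0.918 and 305.5/365 = 0.837.

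If the early share varies from none to all, rather than half, the readings run from 1.57 to 2.25 for M = 119 and from 1.65 to 2.15 for M = 91. The upper ends need every patient to enroll late, with full-year events over 3.2.1 days: 365/305.5 = 1.195, and 365/319.5 = 1.142.

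**Rate ratio.** If controls receive the same dates and the same filter, the factor multiplies both rates at a constant rate and cancels, so 1.446 stays 1.446.

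**The case against.** The strongest reply is that the target is stated. Sections 2.1, 6.1 and 6.4 define a rate within the first post-therapy year, which implies person-time within that year. Section 3.2.1 sits under a participation heading and can be read as describing contact rather than the denominator. Infectious history before enrollment is collected, so full-year capture is plausible, and under 3.2.1 with symmetric enrollment that gives no cohort bias.

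Much of this stands. A reader might infer that Aim 1 has no time window at all; those sections rule that out. What remains is that no text turns the stated target into a day count, and the sections that do give dates contradict each other.

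A reader might also infer that the rate ratio is diluted. If ALL infections were restricted to post-enrollment, first-year time while controls were counted in full, the M = 119 figures would turn 1.45 into 1.73/1.30 = 1.33 or 1.57/1.30 = 1.21. The documents do not support this. The abstract and section 2.1 compare the groups over the same period, the abstract and 6.3.4 give controls the same one-year period, and 7.1 promises the same infection data for controls. Only a literal reading of the 3.2.1 control sentence leaves room for a mismatch.

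**Conclusion.** The point holds as a mismatch between a stated target and the person-time rules meant to deliver it. Follow-up days are undefined in 6.3.2, the only stated start is enrollment, and 3.2.1 and 4.3 give end dates that differ by up to about 91 or 119 days. The per-patient windows (246 to 484 days under 3.2.1, and up to a third of days outside the target year under 4.3) follow directly from the documents, taking three months as 91 days and the four weeks as widening the window.

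A reader might go further and conclude that the primary rate will be biased. The documents do not establish this. Direction and size depend on enrollment timing, which is not given. The cohort figures rest on an assumed constant rate and an assumed enrollment pattern, and two of the four readings return exactly 1.88. What is established is that the same data can yield different primary rates under the text as written, and that the window behind the preliminary 1.88 is not stated.

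**What to change.** - Reconcile the end dates in 3.2.1 and 4.3.
- In 6.3.2, use one window for both events and days. Exclude everything before end of therapy, and end at the earliest of day 365 after end of therapy, loss to follow-up or death.
- Prespecify the start: either end of therapy, with chart-abstracted events and the matching days, or the later of end of therapy and enrollment. Report the other as a sensitivity analysis. Statisticians differ on which should be primary. Starting at end of therapy uses the full year, but it relies on charts without monthly contact and credits late enrollees with time during which they had to be relapse-free to qualify (3.3.2). Delayed entry avoids this but loses early weeks.
- State how time after relapse is counted; 6.3.2 censors only at loss to follow-up or death.
- Give matched controls the same calendar dates and counting rule, fixed before their data are pulled.
- State which window produced the preliminary 1.88.

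**Cost.** Wording in three sections and a date filter. The end-of-therapy date is already abstracted (3.2.1), and control data are collected only once ALL follow-up is complete (6.3.2). Some events and days are dropped. Early enrollees who were stopped at one year from enrollment need chart review for up to 119 further days, or censoring at last follow-up.

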#### **3.2.2 Total Number of Study Sites/Total Number of Subjects Projected**

The study will be conducted at seven investigative sites in the United States. Other sites may be added in the future. It is expected that approximately 115 subjects will be enrolled over the course of this study to produce 110 evaluable subjects. Evaluable patients will be defined as patients that are enrolled and at least one blood specimen collected.

For each of the 110 enrolled evaluable subjects in the ALL cohort, at the end of the follow-up period, three age- and sex-matched healthy control patients will be selected for comparison, to assemble a cohort of 330 total healthy control patients. The full cohort,

---

including both ALL patients and 3:1 matched controls, is anticipated to include 440 evaluable patients.

### **3.3 Study Population**

#### **3.3.1 Inclusion Criteria for ALL Cohort**

1. Children, adolescents, and young adults ages 3 years to 31 years diagnosed with B or T ALL at age 12 months or older
2. Completed ALL chemotherapy within the past three months or will complete ALL chemotherapy in the upcoming three months (+/- 4 weeks)
  - **Blinatumomab sub-cohort (n = 20-25):** received ALL chemotherapy including the monoclonal antibody blinatumomab
3. Three years of age or older at time of enrollment.

#### **3.3.2 Exclusion Criteria for ALL Cohort**

- 1) Diagnosis of infant ALL
- 2) Evidence of disease relapse
- 3) History of primary immunodeficiency (except related to Down Syndrome)
- 4) History of a stem cell transplant or cellular immunotherapy
- 5) History of prior malignancy or condition requiring chemotherapy other than for current ALL diagnosis.

Subjects that do not meet all the enrollment criteria may not be enrolled. Any violations of these criteria must be reported in accordance with IRB Policies and Procedures.

#### **3.3.3 Inclusion/Exclusion Criteria for Matched Healthy Controls Cohort**

Matched healthy control patients will be selected based on age- and sex-matching to ALL cohort patients. All healthy patients who received care at the Children's Hospital of Philadelphia beginning in 2022 during the follow-up period that the ALL cohort patients are followed for the study will be eligible for inclusion in the matched cohort.

Patients with a history of any oncologic diagnosis or other condition that could predispose them to a higher risk of infection (e.g., primary immunodeficiency except related to Down syndrome, receipt of chemotherapy or immunomodulating drugs for treatment of any condition, etc.) will be excluded from the healthy controls cohort to ensure a comparator group that mirrors the typical population of healthy children as closely as possible.

## **4 STUDY PROCEDURES**

### **4.1 Screening**

A registry of patients diagnosed with ALL that are expected to complete therapy on or after December 1, 2021 will be complied to identify potentially eligible patients. Subjects will be screened for eligibility in accordance with inclusion and exclusion criteria outlined in section 3.3. The following will be performed during screening:

- Medical record review to identify potentially eligible patients
- Completion of a screening log for all screened patients to ensure study eligibility
- Approach eligible patients for informed consent and, if appropriate, child assent

### **4.2 Visit schedule**

#### **4.2.1 Visit**

Once enrolled, subjects will have a baseline visit, followed by in-person visits at approximately 3, 6, and 12 months. Prior to or at the time of the baseline visit, vaccination records will be obtained. At the baseline and follow-up visits an interim infectious history will be obtained. Patients will have blood drawn for research assays as detailed below at 3-, 6-, and 12-month visits.

### **4.3 Observational Period**

Patients will be followed up to approximately one year from enrollment. Patients will also have specified relevant data collected from prior to the day of enrollment. During the observational period, the following will be performed:

- Data abstraction from the Medical Record

